8.1.1 Route and method of administration

A manual for alirocumab administration (injection instruction manual) will be provided to investigators (or parents/patients according to the phase of the study) containing detailed instructions on use.

During the main treatment dose finding study period for Cohorts 1 and 2, the injections will be administered by the staff at the clinical site or by a trained health care professional at home for visits Week 2 and Week 6, the injections at Week 0 and 4 will be administered at the clinical site by the study staff. For Cohort 3 the injections at Week 0, and at Week 4 will be administered at the clinical site by the study staff. For Cohort 4, the injections at Week 0, Week 4, and Week 8 will be administered at the clinical site by the study staff. During the open-label extension, alirocumab could be administered at clinical site or by study nurse at home or by self-injection or by another designated person (such as a parent, etc...) depending on availability or not of the prefilled syringes. The used syringe will be discarded in a sharps container which will be provided to staff site/nurse/patients. It is recommended that alirocumab injections be rotated within an anatomical area (eg, right thigh then left thigh or right abdomen then left abdomen). Staff site/Nurse/Patients also have the option to inject in a different anatomical area (eg, thigh then abdomen) during the study. If another concomitant drug or vaccine is being injected at the same site planned for alirocumab injection, then the staff site/nurse/patient should be advised to use an alternate location for administration of alirocumab.

IMP must be stored between $+2^{\circ}\text{C}$ and $+8^{\circ}\text{C}$, and administered at room temperature. Specific information regarding dose preparation and administration is given in the relevant manuals.

Instructions as outlined in the relevant manuals should be provided to the investigator/nurse (or another designated person who will administer the injections) at training and as needed during the course of the study. Close supervision and feedback should be given at the training visit if applicable and other visits as needed. Anyone that plans to administer IMP must be trained by the study staff.

8.1.2 Timing of administration

During the main dose finding treatment period the first alirocumab injection for each cohort will start at Week 0 (after each respective screening period and DMC agreement for Cohorts 2 and 3) as soon as possible after the call for inclusion using the treatment kit number provided by the IRT according to cohort number and body weight. The first injection after call for inclusion will be done at the site by the investigator staff. Patients will be monitored at the investigational site for at least 30 minutes after this first injection.

The investigator staff will administer subsequent injections on site at the clinic, according to the dosing schedule at approximately the same time of the day. On days where the clinic study visit coincides with dosing, the dose of study drug will be administered after all study assessments have been performed and all laboratory samples (including PK) collected. For visits where home injection is allowed, the health care professional will administer the injection at the patient's home, as described in the relevant manuals.

During the main dose finding treatment period, alirocumab will be administered subcutaneously every 2 weeks or every 4 weeks at approximately the same time of the day; however it is acceptable to have a window period of ± 3 days.

Follow-up period during the main phase without treatment

No alirocumab administration between W8 and W16 for Cohort 1.

No alirocumab administration between W8 and W16 for Cohort 2.

No alirocumab administration between W8 and W14 for Cohort 3.

There is no follow up period for Cohort 4.

During the open-label extension period for Cohorts 1 & 2 the first injection administration will start at Week 16 after the last injection administration at Week 6 (ie, 10 weeks after the last administration of alirocumab. The treatment kit(s) number(s) will be provided by IRT according to the last dose administered in Cohort1/Cohort 2. The first injection of the extension period will be done at the site by the investigator staff. If the self-injections by patient or another designated person (such as parent, nurse, etc.) are decided during the extension period a training injection should be planned 2 weeks before the first self-injection, under direct site staff supervision.

During the open-label extension period for Cohort 3, the first injection administration will start at Week14 after the last injection administration at Week 4 (ie, 10 weeks after the last administration of alirocumab). The treatment kit number will be provided by IRT according to the last dose administered in Cohort 3. The first injection of the extension period will be done at the site by the investigator staff. If the self-injections by patient or another designated person (such as parent, nurse, etc.) are decided during the extension period a training injection should be planned 4 weeks before the first self-injection, under direct site staff supervision.

During the open-label extension period for Cohort 4, the first injection administration will start at Week 12 at the end of the 12-week open-label dose finding. The treatment kit number will be provided by IRT according to the last dose administered in Cohort 4. The first injection of the extension period will be done at the site by the investigator staff. If the self-injections by patient or another designated person (such as parent, nurse, etc.) are decided during the extension period a

training injection should be planned 4 weeks before the first self-injection, under direct site staff supervision.

During the extension treatment period, IMP should ideally be administered every 2 weeks SC or every 4 weeks at approximately the same time of the day; however it is acceptable to have a window period of ± 3 days. The time of the day is based on visit's time or patient's preference in case of self-injections.

If by mistake or due to other circumstances an injection is delayed by more than 7 days or completely missed (for Cohorts 1 and 2) or by more than 14 days or completely missed (for Cohort 3 and Cohort 4), then the patient should return to the original schedule of study treatment administration without administering delayed injections. On the other hand, if the delay is less than or equal to 7 days (for Cohorts 1 and 2) from the missed date or if the delay is less than or equal to 14 days for (Cohort 3 and Cohort 4) from the missed date, then the patient should administer the delayed injection and then resume the original schedule of study treatment administration.

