The addition to the higher doses in the Q4W cohort with extended 12 week study duration (including 2 new visits at Week 10 and Week 12) for the open label dose-finding period will more appropriately ensure that steady state has been reached after 3 alirocumab injections (2 interdose intervals) in terms of PK and LDL-C and related parameter reduction efficacy. An intermediate visit between the dosing interval (Week 10) is specifically introduced to better document the PK and LDL-C data from the Q4W dosing regimen that is known to show some peak-trough variability over the 4-week dosing interval, ie, a peak in the decrease at the mid dosing interval time point and trough reduction in LDL-C at the end of dosing interval time period. Thus, extending the duration of a higher Q4W dosing regimen to 12 weeks (an additional 4 weeks) will secure more comprehensively data on the LDL-C related profile reduction potential of a Q4W dosing regimen for alirocumab.

Given the 12 week duration, only LDL-C and key related parameters (TC, non-HDL-C, and TG) will be measured at Week 10 and Week 12 to minimize blood collection. The post-treatment follow-up period is no longer needed based on the data collected from the previous 3 cohorts.

All patients in Cohort 4 will receive alirocumab at 150 mg Q4W for BW <50 mg/300 mg Q4W for BW \geq 50 kg using prefilled syringes.

Cohort 4, similar to the other cohorts, will include alirocumab administration during the open-label extension that will continue until approximately 10 weeks before the initiation of the pediatric phase 3 study or December 2018 at the latest. The patients, after a wash-out period of at least 10 weeks after the last injection of alirocumab, will have the opportunity to participate in the phase 3 study. Though Cohorts 1 to 3 will be switched to the optimal regimen selected for the phase 3 study, Cohort 4 will remain on their initial regimen given the planned study end date of December 2018.

Conclusion on the benefit risk assessment with alirocumab:

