For Cohorts 1 to 3, alirocumab injections may be prepared from vials by the pharmacist (or equivalent) or supplied as prefilled syringes (PFS) depending on availability and additional considerations.

If the PFS is available in the extension phase, then patients may either switch from alirocumab injections prepared from vials to PFS or directly initiate PFS (depending on patient's date of entry into the extension phase). After appropriate training, the parent/guardian or patient (if appropriate) will administer the PFS at home or another preferred location. In certain cases, alternative arrangements may be made for the administration of alirocumab with PFS.

If the PFS is not available in the extension phase for Cohorts 1 to 3, then alirocumab injections prepared from vials will be administered at the clinical site (by the site staff) or at the patient's home or another preferred location contingent upon alternative arrangements being made for such an administration.

The alirocumab dose/dose regimen received during the open-label dose finding treatment period of the main phase will be continued every 2 weeks or every 4 weeks during the OLE period, since [REDACTED].

However, once the final optimal doses for the Phase 3 study are selected, and if device is available, then these final optimal doses from the Q2W or Q4W regimen will be administered to all patients in Cohorts 1 to 3 during the OLE period, based on their body weight at the time of the dose change.

For Cohorts 1 & 2: The study treatment is a single SC injection of 0.5 mL for 30, 40, 50 or 75 mg dose of alirocumab (according to the last dose in each cohort and DMC recommendations) provided in a prefilled syringe or in a syringe (extracted from vial), administered every 2 weeks in the abdomen, thigh, or outer area of the upper arm. Study drug will be administered by SC injection Q2W, starting at Week 16 and continuing up to the last injection, 2 weeks before the end of the open-label extension period.

For Cohort 3: The study treatment is a single SC injection of 1 mL for 75 or 150 mg dose of alirocumab (according to the body weight, the last dose and DMC recommendations) provided in a prefilled syringe or in a syringe (extracted from vial), administered every 4 weeks in the abdomen, thigh, or outer area of the upper arm. Study drug will be administered by SC injection Q4W, starting at Week 14 and continuing up to the last injection, 4 weeks before the end of the open-label extension period.

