For Cohort 4, sterile alirocumab drug product will be supplied at a concentration of 150 mg/mL as 1 mL volume in a prefilled syringe (PFS).

For Cohort 4: The study treatment is a single SC injection of 1 mL for 150 mg dose of alirocumab and 2 injections of 1 mL containing 150 mg each to provide a total 300 mg dose (2 mL) of alirocumab through PFS, administered every 4 weeks in the abdomen, thigh, or outer area of the upper arm. Study drug will be administered by SC injection Q4W, starting at Week 12 and continuing up to the last injection, 4 weeks before the end of the open-label extension period.

Dosing for the open-label extension treatment period should ideally be administered Q2W SC or Q4W SC at approximately the same time of the day; however, it is acceptable to have a treatment window of ± 3 days. The time of day is based on the patient's preference.

Alirocumab administration will continue until at least 10 weeks before the initiation of the pediatric Phase 3 study in the site where the patient is potentially participating or December 2018, whichever comes first.

In the event an injection is delayed by more than 7 days or is completely missed, the patient should return to the original schedule of study drug dosing without administering additional injections. If the delay is less than or equal to 7 days from the missed date, the patient should administer the delayed injection and then resume the original dosing schedule.

Detailed instructions for transport, storage, preparation, and administration of IMP will be provided by the site to the patient/caregiver.

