8.5 PACKAGING AND LABELING

Open Label dose finding treatment period:

For Cohorts 1, 2 and 3: Each kit will contain one vial: either a vial of alirocumab 150 mg/mL or a vial solvent for alirocumab. The number of kits and types of kits (active or solvent) to be dispensed depend on the treatment doses / dose regimen (see [Table 1](#)).

For Cohort 4, patients will receive 1 or 2 kit(s) for the 12 week alirocumab treatment period depending on the dose group (1 kit for 150mg Q4W & 2 kits for 300mg Q4W). Each kit will contain 4 PFS of alirocumab 150 mg/mL

Open Label Extension period:

If PFS are available:

Cohorts 1 & 2: patients will receive 2 kits for 12-weeks alirocumab treatment period. Each kit will contain 4 PFS.

Cohort 3: patients will receive 1 kit for 12-weeks alirocumab treatment period. Each kit will contain 4 PFS.

Cohort 4: patients will receive 1 or 2 kit(s) of PFS for up to a 12 week alirocumab treatment period, depending on dose group.

If PFS are not available for Cohorts 1 to 3:

The packaging will be the same as for Open Label Dose finding:

Each kit will contain one vial: either a vial of alirocumab 150 mg/mL or a vial solvent for alirocumab. The number of kits and types of kits (active or solvent) to be dispensed depend on the treatment doses / dose regimen (see [Table 1](#)).

Packaging is in accordance with the administration schedule. The content of the labeling is in accordance with the local regulatory specifications and requirements.

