- The alirocumab injections should be done every 2 weeks for Cohorts 1 and 2 or every 4 weeks for Cohort 3 and Cohort 4 at clinical site, by a health care professional at patients' home, or by patient or representative (parent...) at home according to the type of supplied syringe (prefilled or not) during all the extension period. This alirocumab administration during the open-label extension will continue until approximately 10 weeks before the initiation of the pediatric Phase 3 study or December 2018, at the latest.

**10.1.4.2 Visit 9/Week 20 for Cohorts 1 & 2 /Week 18 for Cohort 3/Week 16 for Cohort 4
(Phone Call Option)**

- Collect AEs.
- Record concomitant medication.
- Review patient's diet. Patient should be on a diet in accordance with the American Academy of Pediatrics guidelines (1) or equivalent.
- Review patient's diary and compliance check of IMP if applicable.
- Check of stability of LMT dosing.
- Reminders:
 - An appointment will be given for the next study site visit,
 - Patient to bring the diary, and used and unused kits, at the next study site visit (if applicable ie, prefilled syringes).

**10.1.4.3 Visit 10/Week 24 for Cohorts 1 & 2 /Week 22 for Cohort 3/Week 20 for Cohort 4
(Phone Call Option)**

- Collect AEs.
- Record concomitant medication.
- Review patient's diet. Patient should be on a diet in accordance with the American Academy of Pediatrics guidelines (1) or equivalent.
- Check of stability of LMT dosing.
- Reminders:
 - An appointment will be given for the next study site visit,
 - Remind patient to be in fasting conditions (ie, overnight, at least 8 hours fast and refrain from smoking) for next study site visit. Also, alcohol consumption within 48 hours and intense physical exercise within 24 hours preceding the next study site visit are discouraged,
 - Patient to bring the diary, and used and unused kits, at the next study site visit (if applicable ie, prefilled syringes).

10.1.4.4 Visits 11, 13, 15, 17, 19 (every 24 weeks)/ Visit 11 only for Cohort 4

- Collect AEs.
- Record concomitant medication.
- Urine pregnancy test (females who have experienced menarche only).
- Review patient's diet. Patient should be on a diet in accordance with the American Academy of Pediatrics guidelines (1) or equivalent.

- If the prefilled syringe becomes available: Data collection on alirocumab administration and alirocumab compliance check by review of diary and treatment kit accountability for Cohorts 1 to 3.

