 - An overdose (accidental or [intentional]) is an event suspected by the Investigator or spontaneously notified by the patient (not based on systematic injection counts) and defined as at least twice of the intended dose within the intended therapeutic interval (ie, 2 or more injections from the treatment kit are administered in <7 calendar days for Q2W regimen or 2 or more injections from the treatment kit are administered in <14 calendar days for Q4W regimen) to be reported using the corresponding screens in the eCRF using the term "symptomatic overdose (accidental [or intentional])". The patient should be monitored and appropriate symptomatic treatment instituted if needed,

- The circumstances of the overdose should be clearly specified in the verbatim,
- Neurologic Events:
 - Neurologic Events that require additional examinations/procedures and/or referral to a specialist should be reported as an AESI. If the event does not require additional examinations/ procedures and/or referral to a specialist, it should be reported as a standard AE.
- Neurocognitive events:
 - All neurocognitive events will be considered as AESI.

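### Protocol 8.1 and 8.1.2 give opposite instructions for an extension injection 8 to 14 days late in Cohorts 3 and 4 (minor)

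*Protocol*

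**What the plan says.** Two places in the protocol state a late-dose rule for the open-label extension.

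- Section 8.1, under its extension heading, names no cohort or regimen: "In the event an injection is delayed by more than 7 days or is completely missed, the patient should return to the original schedule". A delay of 7 days or less means the injection is given.
- Section 8.1.2, directly after its paragraph on extension dosing, splits by cohort. Cohorts 1 and 2 have a 7-day limit. Cohorts 3 and 4 give the late injection "if the delay is less than or equal to 14 days for (Cohort 3 and Cohort 4) from the missed date".

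Most of the operational text treats Cohort 3 as a Q4W cohort. Section 10.1.4 says "The alirocumab injections should be done every 2 weeks for Cohorts 1 and 2 or every 4 weeks for Cohort 3 and Cohort 4". Section 8.1 says of Cohort 3 "Study drug will be administered by SC injection Q4W, starting at Week 14 and continuing up to the last injection". Section 8.5 supplies on the same footing: "Cohort 3: patients will receive 1 kit for 12-weeks alirocumab treatment period. Each kit will contain 4 PFS".

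The protocol also provides for a switch. Section 4 says "Though Cohorts 1 to 3 will be switched to the optimal regimen selected for the phase 3 study", and Section 8.1 says that, once doses are selected and if the device is available, "these final optimal doses from the Q2W or Q4W regimen will be administered to all patients in Cohorts 1 to 3 during the OLE period". The SAP uses Q2W conventions for these patients. Section 2.1.4 ends the combined treatment period 21 days after the last injection for switched Cohort 3 patients, and Section 2.4.3.1 adds 14 days for exposure after the switch. Cohort 4 is not switched.

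**The concern.** A late-dose rule should give one answer for a given patient and a given delay. Here a Cohort 3 or 4 patient whose extension injection is 8 to 14 days late is told to skip it in one section and to take it in the other. Both rules sit in extension text, so they cannot be separated as one for the main phase and one for the extension, and no order of precedence is stated.

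Two things are at stake. On Q4W, the choice sets how long the child goes between injections. Section 4 already suggests that the Cohort 3 doses were too low to hold the LDL-C reduction over the whole interval. After a switch to Q2W, a limit attached to the cohort label instead of the current regimen could bring two injections close together. Parents or patients may inject at home with prefilled syringes, so a conflict in the source text can pass into the instructions they receive.

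**Working it through.** The plan gives no figure to reproduce; the check is day arithmetic.

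**Inputs.** Intervals of 28 days (Q4W) and 14 days (Q2W). Limits of 7 days (8.1, all patients) and 14 days (8.1.2, Cohorts 3 and 4). Ten planned patients per cohort.

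**Formulas.** For an injection *d* days late on an interval of *I* days:
- gap before the late injection = *I* + *d*
- days from it to the next nominal dose = *I* − *d*
- gap if it is skipped = 2 × *I*

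**Where the rules differ.** For *d* ≤ 7 both say give. For *d* > 14 both say skip. For *d* = 8 to 14, 8.1 says skip and 8.1.2 says give.

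| Regimen | If given: gap before | If given: days to next nominal dose | If skipped |
|---|---|---|---|
| Q4W, *d* = 8 | 28 + 8 = 36 | 28 − 8 = 20 | 56 |
| Q4W, *d* = 14 | 28 + 14 = 42 | 28 − 14 = 14 | 56 |
| Q2W, *d* = 8 | 14 + 8 = 22 | 14 − 8 = 6 | 28 |
| Q2W, *d* = 13 | 14 + 13 = 27 | 14 − 13 = 1 | 28 |
| Q2W, *d* = 14 | 14 + 14 = 28 | 14 − 14 = 0 | 28 |

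The last row is best set aside. A Q2W injection 14 days late falls on the day of the next one and is more naturally called completely missed, which both sections skip. The usable Q2W range is therefore 6 to 1 days. It assumes the next dose is given on its nominal day; the ±3 day dosing window could shorten or lengthen it.

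**What the cohort label means.** Over 12 weeks Q4W needs 12/4 = 3 syringes and Q2W needs 12/2 = 6. One kit of 4 covers the first and not the second. This supports reading Cohort 3 in 8.1.2 as shorthand for Q4W.

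**Patients.** Cohorts 3 and 4: 10 + 10 = 20 planned, if all enter the extension. The Q2W case concerns Cohort 3 only, about 10.

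**Dose in the short-interval case.** Assume the Phase 3 Q2W doses lie within those tested here. Two doses then total 2 × 30 to 2 × 40 = 60 to 80 mg below 50 kg, and 2 × 50 to 2 × 75 = 100 to 150 mg at 50 kg or more. One Cohort 4 dose is 150 mg or 300 mg in the same weight bands.

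**Limit tied to the regimen.** Q2W with *d* ≤ 7 leaves at least 14 − 7 = 7 days. Q4W with *d* ≤ 14 leaves at least 28 − 14 = 14 days.

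**The case against.** The best defence is that 8.1.2 plainly means 7 days for Q2W and 14 days for Q4W. The rest of the protocol uses Cohort 3 for Q4W patients, so a child moved to Q2W would naturally follow the Q2W limit and the short interval would never arise. Reaching it takes a Q2W choice for Phase 3, an available device, an actual switch, an injection 8 to 14 days late, and a site applying the cohort label literally. This stands, and it makes the short interval a remote case. It does not remove the conflict, because on that same reading a Q4W patient 10 days late is still told to skip by 8.1 and to inject by 8.1.2.

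A reader might infer that a switched Cohort 3 patient has no late-dose rule at all. The documents do not support that: the 8.1 rule covers every extension patient and gives 7 days, which suits Q2W. The trouble is only that 8.1.2, taken literally, disagrees.

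A reader might also infer that two injections within a week would be a protocol-defined overdose. Spacing under 7 days on Q2W meets the interval part of the definition in 10.4.1.3. But the event must be "suspected by the Investigator or spontaneously notified by the patient (not based on systematic injection counts"), and the adverse event of special interest is symptomatic overdose. Close spacing is not enough by itself.

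Finally, separate administration manuals may give a single rule. They are not among the documents reviewed, so the conflict is shown for the protocol text only.

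**Conclusion.** The conflict is real, and its severity is minor. For extension injections 8 to 14 days late in Cohorts 3 and 4, the protocol states two incompatible rules. On Q4W this decides between one 36 to 42 day gap and one 56-day gap, and at least 14 days remain to the next nominal dose either way. For a Cohort 3 patient switched to Q2W, a literal cohort reading of 8.1.2 would leave about 1 to 6 days, while 8.1 avoids this.

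The counts of about 20 patients, and about 10 for the Q2W case, are upper bounds. They assume that everyone enters the extension, and Cohort 4 patients may go directly to Phase 3. The documents give no frequency of late injections. The likely clinical consequence is limited, given the dose totals above and their assumption about the Phase 3 doses.

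It would go too far to infer an effect on the trial's efficacy conclusions. The primary and secondary endpoints are measured in the main phase, at Week 8 and, for Cohort 4, Week 12. Under SAP 2.4.4.2.4 lipids in the combined main and extension period are summarised descriptively from observed data, with results before and after the switch kept apart for Cohorts 1 to 3.

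**What to change.** State one identical rule in Protocol 8.1 and 8.1.2, tied to the regimen in use when the injection is missed:

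- Q2W: give the injection if it is 7 days late or less; otherwise skip it and return to the original schedule.
- Q4W: give the injection if it is 14 days late or less; otherwise skip it and return to the original schedule.

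This keeps the evident intent of 8.1.2 and gives a switched Cohort 3 patient the Q2W limit without further text. The cost is wording in two sections and a notice to sites, with no extra visits or patients.
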